#### Number of angioedema attacks (per month)

The NNA during the treatment period is the number of angioedema attacks normalized for the number of days the subject participated in the period and multiplied by 30.4:

-	_	+1 30.4
presented to two decimal place.		
The NNA for historical data is the administration, divided by 3.	number of angioedema attack	s during 3 months prior to study drug
	h	
	3	

\\SW20RND01\VistaTempDir\Temp28232\Shire 0624 209 SAP v1 0.docx Document: Version Number:

Author: Version Date: 21Jul2017

Template No: CS\_TP\_BS016 Revision 4

#### **Anatomic location**

The summary of anatomic location will be counted for each of the following location where there is a presence of pain or swelling of any level of severity; mild, moderate or severe at any day during the attack.

- Abdominal/Gastrointestinal
- Genital/Urinary (includes scrotum or vulva)
- Upper airway (includes laryngeal or pharyngeal)
- Cutaneous facial
- Cutaneous extremity or peripheral

The historical data of the typical location of subjects angioedema attacks can be obtained from the Medical/Angioedema History eCRF page.

#### Severity (intensity)

The severity of an attack will be the highest value assigned by the subject to any location at any day during the attack. In order to calculate the average severity of attacks, each mild, moderate, and severe attack will be assigned a score of 1, 2, or 3, respectively. The total severity score will be calculated for multiplying the total number of mild attacks by 1, total number of moderate attacks by 2, and the total number of severe attacks by 3, then adding the results of these three calculations.

The average severity of attack will be summarized. The average severity is derived by dividing the cumulative severity score by the total number of attacks.

For historical data, the average overall severity of subjects angioedema attack are collected in the Medical/Angioedema History eCRF page. The similar scoring system as indicated above will be applied to the average severity level.

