#### 4.2. EFFICACY VARIABLES

#### 4.2.1. Prevention of Angioedema Attacks

The following efficacy endpoints for prevention of angioedema attacks will be assessed:

- The normalized number of angioedema attacks (NNA) recorded during the treatment period, normalized for the number of days the subject participated in the period; and the NNA for historical data normalized for 3 months prior to study drug administration.
- Summary of all attacks during the treatment period and historical 3 month data, including:
  - o Anatomic location.
  - o Severity (intensity).
  - o Average duration of attacks.
  - o Number of angioedema attacks treated with CINRYZE®, non- CINRYZE® C1-INH or not treated with C1-INH (including attacks treated with any medications other than C1-INH or untreated attacks).
- Effects of therapy on quality of life (results of AE-QoL questionnaire).

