### 5. STATISTICAL ANALYSIS

## 5.1. GENERAL METHODOLOGY

Experimental results will be summarized using descriptive statistics according to data type (n, mean, standard deviation or standard error, median, and range for continuous endpoints; number and percent of subjects in each category for categorical endpoints).

The estimated median time to event and its 95% confidence interval (CI) will be calculated (if at least 50% of subjects in the Full Analysis Set achieved the event) using the Kaplan-Meier estimator. The Kaplan-Meier estimates will also be displayed graphically.

All analyses will be presented by C1 Inhibitor 1000U only. Study drug administrations were planned according to subjects age; 500U for Subjects 2 to 5 years of age and 1000U for Subjects 6 years of age and older. However, only the higher dose of 1000U were administered.

Unscheduled visits data will not be included in analysis, otherwise specified. Unscheduled visits data will merely be presented in listings.

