## 5.2. ANALYSIS POPULATIONS

Enrolled subjects are all subjects who signed signed informed consent and completed screening.

All treated subjects (ie, Intent-to-Treat Safety [ITT-S] Population: subjects who receive any amount of study drug) will be included in the safety analyses.

Full Analysis Set Population (defined as subjects who have at least one post baseline efficacy assessment) will be included in the efficacy analyses.

All subjects with evaluable PK/PD profiles (ie, PK/PD Population) will be included in PK/PD analyses as appropriate.

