#### Average duration of attacks (days)

The duration of an attack will be measured from the onset of attacks until complete resolution.

The average duration of attacks is calculated by dividing the cumulative duration of attacks by the total number of attacks during the treatment period.

For the historical data, the average duration of attacks recorded on the Medical/Angioedema History eCRF page will be used.

Number of angioedema attacks treated with rescue medication (per month)

Document: \\SW20RND01\\VistaTempDir\Temp28232\\Shire 0624 209 SAP v1 0.docx

Author: PPD Version Number: 1.0
Version Date: 21Jul2017

Template No: CS TP BS016 Revision 4 Reference: CS WI BS005

1.0

Reference: CS WI BS005

The NNA treated with rescue medication will be summarized for CINRYZE®, non-CINRYZE® C1-INH or not treated with C1-INH (including attacks treated with any medications other than C1-INH or untreated attacks), and is defined as below.

For on treatment attacks, only medication taken after study drug administration and had an indication of 'HAE Management - Acute Treatment' selected on the Prior and Concomitant Medications and Therapy eCRF page will be considered as rescue medications. CINRYZE® will only be considered as a rescue medication when treated for 'Breakthrough Attack Treatment'.

For historical data, only medication prior to the start of study drug administration and had an indication of 'HAE Management - Acute Treatment' selected on the Prior and Concomitant Medications and Therapy eCRF page will be considered as rescue medications.

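### On-treatment average severity and duration omit attack-free subjects, while the historical averages cover essentially everyone, so the two periods can describe different people

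*SAP*

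**What the plan says.** SAP 4.2.1 lists, among the prevention endpoints: "Summary of all attacks during the treatment period and historical 3 month data, including" location, severity, average duration and attacks by type of treatment. The derivations in SAP 5.7.1 then define severity and duration separately for the two periods.

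- **Severity on treatment.** "The severity of an attack will be the highest value assigned by the subject to any location at any day during the attack". Mild, moderate and severe attacks score 1, 2 and 3, and "The average severity is derived by dividing the cumulative severity score by the total number of attacks".
- **Severity, historical.** "For historical data, the average overall severity of subjects angioedema attack are collected in the Medical/Angioedema History eCRF page", and the same 1 to 3 scoring is applied to it.
- **Duration on treatment.** "The average duration of attacks is calculated by dividing the cumulative duration of attacks by the total number of attacks during the treatment period".
- **Duration, historical.** "For the historical data, the average duration of attacks recorded on the Medical/Angioedema History eCRF page will be used".

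On who is analysed, SAP 5.2 says: "Full Analysis Set Population (defined as subjects who have at least one post baseline efficacy assessment) will be included in the efficacy analyses". Having an attack is not a condition. SAP 7.1 imputes only missing AE severity and AE causality. SAP 5.1 asks for "n, mean, standard deviation or standard error, median, and range for continuous endpoints". Protocol 4.1, inclusion criterion 5, requires a monthly average of one or more attacks over the 3 months before enrollment.

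**The concern.** Becoming attack-free is what prophylaxis aims for. A subject who succeeds counts as zero in the NNA but has no on-treatment severity or duration, because the denominator is zero. The same subject still has a historical severity and duration. The historical figure then describes the whole group, and the on-treatment figure describes only those who still had attacks.

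If the subjects who became attack-free had milder or shorter attacks before the study, the remaining attacks look worse on average; if they had more severe or longer ones, the remaining attacks look better. Neither pattern would say anything about change within a subject. In a single-arm study of about 6 subjects, one or two such subjects are enough to move a mean visibly, and a reader of the study report could take the movement as an effect of treatment on attack severity or duration.

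**Working it through.** The plan gives no figure on this point, so there is none to reproduce. The check has three steps.

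**1. The definitions.** For an attack-free subject, cumulative score / number of attacks = 0/0, and likewise for duration. No score exists for the absence of an attack, and nothing is imputed. The SAP does not say whether the average is formed per subject or pooled over all attacks. On either reading the attack-free subject adds nothing on treatment. Historically, criterion 5 implies about 3 or more attacks in 3 months, so a value should exist. I say *essentially* everyone because the entry window ends at enrollment while the historical window ends at first dose, and eligibility deviations can occur.

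**2. How likely is an attack-free subject?** Inputs: 6 subjects (minimum completers, Protocol 7.1); 84 days = 84/30.4 = 2.763 months; overseas rate ratio 6.3/12.8 = 0.492 (Protocol 1.1.2), assumed to carry over. Expected on-treatment attacks: mu = monthly historical rate x 0.492 x 2.763. The historical rates and the dispersion k are assumptions. The overseas placebo rate is 12.8/2.763 = 4.63 per month. Poisson: P(0) = exp(-mu). Negative binomial: P(0) = (1 + mu/k)^(-k). Chance of at least one of 6: 1 - (1 - P(0))^6.

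| Historical rate per month | mu | Poisson P(0) | Poisson, at least 1 of 6 | k = 2 | k = 1 |
|---|---|---|---|---|---|
| 1 (entry minimum) | 1.36 | 0.257 | 83% | 93% | 96% |
| 2 | 2.72 | 0.066 | 34% | 70% | 85% |
| 3 | 4.08 | 0.017 | 10% | 50% | 73% |
| 4.63 (overseas placebo) | 6.30 | 0.0018 | 1% | 30% | 59% |
| Two subjects each at 1, 2 and 4.63 | | | 52% | 75% | 87% |

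**3. How far could a mean move?** Take an invented set of historical severities 1, 1, 2, 2, 3, 3 (sum 12, mean 2.00), assume no within-subject change, and give each subject equal weight.

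- One attack-free subject: the on-treatment mean is (12 - 1)/5 = 2.20, (12 - 2)/5 = 2.00 or (12 - 3)/5 = 1.80. It shifts by 0.20 in 4 of 6 cases.
- Two attack-free subjects (15 pairs): the mean is (12 - s)/4, where s is the sum of the pair's scores. The shift is +0.50 once, +0.25 four times, 0 five times, -0.25 four times and -0.50 once: 0.25 or more in 10 of 15 cases, averaging 0.
- Same subjects in both periods: if the two mild subjects become attack-free, the remaining four have a historical mean of (2 + 2 + 3 + 3)/4 = 2.50 and an on-treatment mean of 2.50. The unmatched comparison would show 2.00 against 2.50.

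Pooling changes the on-treatment number again. If those four subjects had 1, 1, 2 and 8 attacks, the pooled severity is (2 + 2 + 6 + 24)/12 = 2.83, against a per-subject mean of 2.50. This is why the averaging unit needs stating.

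**The case against.** **The two averages may not stand in one table.** SAP 5.5 puts historical severity and duration in a separate HAE history table. The attack-summary bullet in SAP 5.7.1 and the title of Table 14.2.1.1 name only the treatment period, and that section uses the language of comparison for the NNA alone. This stands: a reader might infer a side-by-side display, but the table shells are not shown. Nor can it be said from titles alone that no table gives matched values. What remains is that SAP 4.2.1 asks for both periods and SAP 5.7.1 defines a historical counterpart for each average. The mismatch exists wherever the two are printed.

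**The exclusion is unavoidable and already visible.** An attack that did not happen has no severity. On a per-subject reading, the reported n reveals how many subjects dropped out, and with about 6 subjects the listings may permit inspection by hand. This is true, but n shows only that subjects are missing. It does not show the historical values of those who remain.

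**The size is soft.** The probabilities run from 1% to 96% on assumed rates and dispersion, and the severity set is invented. Its SD is 0.89, so the standard error of a six-subject mean is 0.37; a shift of 0.20 is 0.55 of that. This stands. A reader might infer a bias in favour of the drug, but the average shift over all cases is zero and the documents give no reason to expect one direction.

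**A paired severity change would not be clean either.** The historical value is a recalled average; the on-treatment value takes the worst location and day of each attack. A change score could be non-zero with no true change. This stands and limits the fix.

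**Historical rescue use.** A reader might infer that 12 months of medication records (Protocol 6.5.1, SAP 5.8.7) feed a 3-month rate, overstating it up to 4-fold (12/3). The documents do not support this: SAP 4.2.1 places the treated-attack count under the 3-month historical data, and the NNA derivation fixes that window. How a historical medication record is tied to an attack is not stated, but the HAE History Detail data (Listing 16.2.4.3.2) might do it and cannot be seen. This is a request for clarification only.

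**Conclusion.** The point holds and is minor. As defined, the on-treatment averages describe only subjects who still had attacks, and the historical averages describe essentially all subjects. Once anyone is attack-free, the two can differ through composition alone. That conclusion rests only on the SAP's definitions, the absence of imputation and the entry criterion.

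Its size rests on assumptions: the overseas rate ratio, the assumed historical rates and dispersion, equal weighting of subjects, and an invented severity set. On those, an attack-free subject is likely near the entry minimum and unlikely under Poisson at the overseas placebo rate. A composition shift of 0.20 to 0.50 on a 1 to 3 scale is possible in either direction. The effect is confined to descriptive secondary rows. The NNA and the 50%, 70% and 90% responder counts are unaffected, since an attack-free subject has a defined NNA of zero.

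**What to change.** Keep the planned rows and make these changes to SAP 5.7.1 and the table shells:

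1. State whether average severity and duration are formed per subject or pooled over attacks.
2. Add the historical and on-treatment averages of both measures for the same subjects, namely those with one or more on-treatment attacks, and give the number of attack-free subjects.
3. For duration, add the within-subject change. For severity, show the two values without a change score, with a footnote that one is a recalled average and the other is built from the worst location and day of each attack.
4. As a clarification only, repeat the 3-month window in the historical rescue-medication rule and say how historical medication records are linked to attacks.

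Items 1 to 3 use data the plan already collects, and item 4 is wording. The cost is a few extra rows resting on a very small subset, which should be read as description only.

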#### Average duration of attacks (days)

The duration of an attack will be measured from the onset of attacks until complete resolution.

The average duration of attacks is calculated by dividing the cumulative duration of attacks by the total number of attacks during the treatment period.

For the historical data, the average duration of attacks recorded on the Medical/Angioedema History eCRF page will be used.

Number of angioedema attacks treated with rescue medication (per month)

Document: \\SW20RND01\\VistaTempDir\Temp28232\\Shire 0624 209 SAP v1 0.docx

Author: PPD Version Number: 1.0
Version Date: 21Jul2017

Template No: CS TP BS016 Revision 4 Reference: CS WI BS005

1.0

Reference: CS WI BS005

The NNA treated with rescue medication will be summarized for CINRYZE®, non-CINRYZE® C1-INH or not treated with C1-INH (including attacks treated with any medications other than C1-INH or untreated attacks), and is defined as below.

For on treatment attacks, only medication taken after study drug administration and had an indication of 'HAE Management - Acute Treatment' selected on the Prior and Concomitant Medications and Therapy eCRF page will be considered as rescue medications. CINRYZE® will only be considered as a rescue medication when treated for 'Breakthrough Attack Treatment'.

For historical data, only medication prior to the start of study drug administration and had an indication of 'HAE Management - Acute Treatment' selected on the Prior and Concomitant Medications and Therapy eCRF page will be considered as rescue medications.

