6.12.1 Treatment of Breakthrough Angioedema Attacks

A breakthrough attack is defined as an angioedema attack that occurs during long-term prevention therapy with CINRYZE. If a subject receives CINRYZE for treatment of a breakthrough angioedema attack, they should continue their protocol-defined treatment schedule without alteration regardless of when the supplemental dose is administered.

If a breakthrough angioedema attack occurs during the 12-week treatment period through 1-week post-treatment, a supplemental dose of CINRYZE may be administered by IV infusion for treatment of the attack either by the Investigator (or qualified delegate) or subject (or caregiver) if trained and deemed independent to self-administer (1000 U for subjects ≥6 years of age or 500 U for subjects 2-5 years of age). If the subject does not adequately respond to the initial dose within 1 hour, a second dose of CINRYZE may be administered (1000 U for subjects ≥6 years of age or 500 U for subjects 2-5 years of age).

It is recommended that treatment of breakthrough attacks occurs at the investigational site whenever possible so that clinical assessments can be completed as specified. It is preferred that subjects receive CINRYZE within 4 hours but not more than 8 hours after the onset of breakthrough attack symptoms if treatment can occur at the investigational site.

Subjects (at least 12 years of age or their caregivers) who have completed the required self-administration training and deemed independent (per criteria specified in Section 5.3.1) may elect to self-administer CINRYZE for a breakthrough attack. Note: Subjects (or caregivers) who are participating in self-administration training and not yet qualified as independent cannot self-administer CINRYZE for a breakthrough attack; rather they must seek treatment at the investigational site. If a subject (or caregiver) who self-administers CINRYZE for treatment of a breakthrough attack does not respond adequately after instructed treatment (ie, 2 doses separated by 1 hour), they should notify the Investigator and seek medical attention or report to study site to seek further treatment and relief of symptoms.

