#### 5.7.2. TREATMENT OF BREAKTHROUGH ANGIOEDEMA ATTACKS

A breakthrough attack is defined as an angioedema attack that occurs during long-term prevention therapy with CINRYZE® (i.e, between first study drug and last study drug dose).

The following efficacy endpoints for treatment of breakthrough angioedema attacks will be assessed by CINRYZE® treated attacks, non-CINRYZE® C1-INH treated attacks and all other attacks (including any medications other than C1-INH and untreated attacks):

- The number of subjects with breakthrough angioedema attacks.
- The number of subjects with 1, 2, 3 or more angioedema attacks.
- The number of subjects who achieve initial improvement and Complete Resolution.
- Time to initial improvement and time to Complete Resolution.

Additional analysis for breakthrough angioedema attacks treated with CINRYZE® will also be presented for:

- The number of subjects with breakthrough angioedema attacks.
- The number of subjects with 1, 2, 3 or more angioedema attacks.
- Time from onset of attack to time treated by CINRYZE.
- The number of subjects who achieve initial improvement and Complete Resolution. Complete Resolution is defined as the cessation of all symptoms of the breakthrough angioedema attack since onset of attack.
- Time from the start of study drug administration, CINRYZE°, for the particular attack to the time of initial improvement and time to Complete Resolution.

\\SW20RND01\\VistaTempDir\Temp28232\Shire\_0624\_209\_SAP\_v1 0.docx Document: Version Number:

Version Date: 21Jul2017

Template No: CS\_TP\_BS016 Revision 4

Effective Date: 01Apr2016

Author:

Copyright © 2009, 2010, 2012, 2016 Quintiles Transnational Corp. All rights reserved.

The contents of this document are confidential and proprietary to Quintiles Transnational Corp. Unauthorized use, disclosure or reproduction is strictly prohibited.

Shire
PROTOCOL: 0624-209
Page 18 of 35

Derivations will be constructed as follow:

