#### **Time to Complete Resolution**

Time to complete resolution is defined as the time from the onset of attack to complete resolution of symptoms.

The analysis of the time to event endpoint includes only the first attack from each subject meeting the treatment criterion since attacks experienced by the same subject are dependent. Median time to complete resolution and the corresponding 95% CI estimated using the Kaplan-Meier method will be summarized.

Kaplan Meier plots for time from CINRYZE® to initial improvement and to complete resolution will also be presented.

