## 9. APPENDICES

# 9.1. APPENDIX I – LIST OF STATISTICAL OUTPUTS

#### 9.1.1. LIST OF PLANNED TABLES

Table 14.1.1.1 Subject Disposition (All Screened Subjects)

Table 14.1.2.1 Protocol Deviations (Intent-to-Treat Safety Analysis Set)

Table 14.1.4.1 Demographic and Baseline Characteristics (Intent-to-Treat Safety Analysis Set)

Table 14.1.4.3.1 Summary of HAE History (Intent-to-Treat Safety Analysis Set)

Table 14.1.4.3.2 Summary of Medical History (Intent-to-Treat Safety Analysis Set)

Table 14.1.4.4 Prior Medications and Therapy (Intent-to-Treat Safety Analysis Set)

Table 14.1.4.5 Concomitant Medications and Therapy (Intent-to-Treat Safety Analysis Set)

Table 14.2.1.1 Summary of Angioedema Attacks during Treatment Period (Full Analysis Set)

Table 14.2.1.2.1 Sensitivity Analysis Completed Schedules - Summary of Angioedema Attacks during Treatment Period (Full Analysis Set)

Table 14.2.1.2.2 Sensitivity Analysis Treatment Compliance - Summary of Angioedema Attacks during Treatment Period (Full Analysis Set)

Table 14.2.1.3 Analysis of Clinical Responder Rate – Achieving at least 50%, 70% or 90% Reduction Relative to Historical Data in NNA (Full Analysis Set)

Table 14.2.2.1.1 Summary of Breakthrough Angioedema Attacks Treated By CINRYZE (Full Analysis Set)

Table 14.2.2.1.2 Summary of Breakthrough Angioedema Attacks Treated By Non-CINRYZE C1-INH (Full Analysis Set)

Table 14.2.2.1.3 Summary of Other Breakthrough Angioedema Attacks Not Treated with C1-INH (Full Analysis Set)

Table 14.2.2.1.4 Summary and Change from Baseline on AE-QoL (Full Analysis Set)

Table 14.2.3.1 C1-INH Antigen, Functional C1-INH activity, Complement C4 and C1q (Intent-to-Treat Safety Analysis Set)

Table 14.2.3.2 Antibody Results (Intent-to-Treat Safety Analysis Set)

Table 14.3.1.1 Overall Treatment-emergent Adverse Events (TEAEs) (Intent-to-Treat Safety Analysis Set)

Table 14.3.1.2.1 Treatment-emergent Adverse Events by System Organ Class and Preferred Term (Intent-to-Treat Safety Analysis Set)

Document: \\SW20RND01\\VistaTempDir\Temp28232\\Shire\_0624\_209\_SAP\_v1 0.docx

Version Date: 21Jul2017

Version Number:

1.0

Template No: CS TP BS016 Revision 4 Reference: CS WI BS005

Effective Date: 01Apr2016

Author:

Table 14.3.1.2.2 Serious Treatment-emergent Adverse Events by System Organ Class and Preferred Term (Intent-to-Treat Safety Analysis Set)

Table 14.3.1.3.1 Treatment-emergent Adverse Events by Preferred Term (Intent-to-Treat Safety Analysis Set)

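### Attacks are classed by the recorded purpose of C1-INH, so scheduled 1000 U CINRYZE infusions given during an attack go uncounted in all three treatment categories

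*SAP*

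**What the plan says.** SAP 5.7.1, under the derivation for attacks treated with rescue medication, sets three categories: CINRYZE, non-CINRYZE C1-INH, and "not treated with C1-INH (including attacks treated with any medications other than C1-INH or untreated attacks), and is defined as below". The rule for the first is that CINRYZE "will only be considered as a rescue medication when treated for 'Breakthrough Attack Treatment". The test is the recorded purpose of the infusion, not whether an infusion took place during the attack.

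SAP 5.7.2 uses the same split for the treatment endpoints, with a residual group of "all other attacks (including any medications other than C1-INH and untreated attacks". Each category reports "Time to initial improvement and time to Complete Resolution". The main time origin is attack onset: "Time to complete resolution is defined as the time from the onset of attack to complete resolution of symptoms". For CINRYZE-treated attacks the times are also measured from the start of the rescue infusion. The residual group's planned table, 14.2.2.1.3, is titled "Summary of Other Breakthrough Angioedema Attacks Not Treated with C1-INH" (SAP 9.1.1).

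Prophylactic dosing runs alongside, twice weekly for 12 weeks (Protocol 3). After an attack is treated with CINRYZE, Protocol 6.12.1 says of subjects that "they should continue their protocol-defined treatment schedule without alteration regardless of when the supplemental dose is administered". That sentence covers treated attacks only. For attacks given no supplemental dose, the relevant fact is that no section withholds a scheduled infusion while symptoms are present; the symptom-free requirement in Protocol 4.2 applies only before the first dose.

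**The concern.** SAP 5.1 states that only the 1000 U dose was given. For subjects aged 6 or over, Protocol 6.12.1 gives the supplemental attack dose as 1000 U too. The supplemental dose is optional. A subject whose attack begins on or shortly before a dosing day can therefore receive an infusion of the same size as the attack dose, on schedule, while symptomatic, and the attack is tabulated as not treated with C1-INH. Likewise, a rescue-treated attack may receive a scheduled infusion before it resolves, and the resolution time is then credited to the rescue dose alone. No SAP rule flags, separates or censors such attacks.

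Treatment of breakthrough attacks is a stated objective. SAP 6.2 drops the Clinical Relief analysis because too few data were collected, which leaves initial improvement and Complete Resolution as the treatment-response endpoints. In a small descriptive study, table titles and medians carry most of the interpretation.

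**Working it through.** **Inputs from the documents**
- Infusions every 3 or 4 days, 24 doses in 12 weeks (Protocol 3, Schedule 2).
- Average gap between infusions: 3.5 days (SAP 5.8.8).
- Breakthrough attacks fall between first and last study dose (SAP 5.7.2).
- Time-to-event summaries use one attack per subject, the first that qualifies (SAP 5.7.2).
- At least 6 completers (SAP 3.2).

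**Assumptions**
- Gaps alternate 3 and 4 days.
- Attack onset is uniform over the dosing cycle.
- Time from onset to event, D, ranges from 4 hours to 4 days. The documents give no durations, although they record historical duration in days.

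**Step 1. Reproduce the plan's figure.** 7 days / 2 infusions = 3.5, and 84 days / 24 doses = 3.5. It agrees.

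**Step 2. Chance that a scheduled infusion falls within D days of onset.** One cycle is 7 days, with one gap of 3 and one of 4:

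P(D) = [min(D, 3) + min(D, 4)] / 7

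| Onset to event | Substitution | P(D) |
|---|---|---|
| 4 h | (1/6 + 1/6)/7 | 4.8% |
| 8 h | (1/3 + 1/3)/7 | 9.5% |
| 12 h | (0.5 + 0.5)/7 | 14.3% |
| 1 day | (1 + 1)/7 | 28.6% |
| 2 days | (2 + 2)/7 | 57.1% |
| 3 days | (3 + 3)/7 | 85.7% |
| 4 days or more | (3 + 4)/7 | 100% |

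A simulation of 400,000 uniform onsets over a 24-dose schedule (12 × 3 + 11 × 4 = 80 days from first to last dose) gave 4.8%, 14.5%, 28.8%, 57.5%, 86.2% and 100% at 4 h, 12 h, 1, 2, 3 and 4 days. These are within 0.6 percentage points of the formula.

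**Step 3. What this means in a sample of this size.** Suppose a category holds 6 first attacks. This is only an illustration, since subjects need not have an attack in any given category. The expected number affected is 6 × P, and the chance of at least one is 1 − (1 − P)^6:

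| Onset to event | Expected of 6 | At least one |
|---|---|---|
| 4 h | 0.3 | 25% |
| 12 h | 0.9 | 60% |
| 1 day | 1.7 | 87% |
| 2 days | 3.4 | 99% |
| 3 days | 5.1 | about 100% |

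**Step 4. Which endpoints are exposed.** Time to Complete Resolution and attack duration cover the whole interval from onset to resolution, so the day-scale rows apply if attacks last a day or more. Time to initial improvement ends sooner; if improvement comes within hours, the first rows apply and the effect is small.

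**The case against.** The derivation in SAP 5.7.1 is openly about rescue medication and classifies by indication. Every breakthrough attack is by definition on prophylactic CINRYZE, so no category can mean drug-free. No test between categories is planned, and treatment of attacks is not randomised, so any contrast would be confounded anyway. Kaplan-Meier plots are planned only for time from CINRYZE. The protocol's own treatment endpoints concern CINRYZE-treated attacks; the table of attacks without C1-INH is a SAP addition. Listings of infusions and attacks are planned, so overlap could be checked by hand.

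Much of this stands, and it rules out several stronger readings that a reader might infer:
- *That Table 14.2.2.1.3 is simply mislabelled.* In context its title means no C1-INH given to treat the attack. It is incomplete rather than false: taken alone, it can be read as no C1-INH infusion during the attack.
- *That many of these attacks did receive a scheduled dose.* The documents give no durations, so the shares are conditional.
- *That improvement times are affected as much as resolution times.* They are not, if improvement comes within hours.
- *That only the CINRYZE-treated and untreated groups are affected.* A scheduled dose can equally fall inside an attack treated with another C1-INH product.

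SAP 5.7.2 also does not restate the purpose-based rule. Applying it there is the natural reading, since the categories match and no other rule is given, but it is an inference.

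None of this supplies a rule for the overlap. Listings do not qualify a summary median.

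**Conclusion.** The point holds as a gap in the analysis specification. Classification by recorded purpose leaves scheduled infusions uncounted in all three categories. Resolution times and durations therefore describe neither the course without a CINRYZE infusion nor the response to the rescue dose alone.

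Its size depends on attack duration. Under uniform onset and alternating gaps, about 29%, 57% or 86% of attacks lasting 1, 2 or 3 days would contain a scheduled infusion, as would all attacks of 4 days or more. For initial improvement the share is about 5% at 4 h and 10% at 8 h. If attacks cluster late in the dosing interval, the shares would be higher. Given the small sample and the loss of Clinical Relief, the SAP should address this; it does not call the prophylactic dosing into question.

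**What to change.** This changes the analysis only; dosing and rescue rules are untouched.

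1. Keep the indication-based categories, state in SAP 5.7.2 that the 5.7.1 rule applies there, and retitle the third category *No C1-INH given as attack treatment*.
2. In all three categories, flag each attack with a scheduled CINRYZE infusion between onset (or the rescue dose, where that is the time origin) and improvement or resolution. Report the number flagged for each endpoint.
3. Add a sensitivity version of the time-to-event summaries that censors at the first scheduled infusion after the time origin, if it precedes the event. The schedule is set by the calendar rather than by the course of the attack, which makes this a reasonable censoring point.
4. Do not redefine the third group as attacks with no infusion before resolution. That selects on the outcome: under the assumptions above, 86% of 3-day attacks and all attacks of 4 days or more would leave the group, and those remaining would look fast-resolving by construction.

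The inputs are already collected: infusion start and end times (Protocol 5.3), and attack onset, improvement and resolution times (Protocol 6.12.2). The cost is SAP wording, one derived flag per endpoint and a further set of summaries. Censoring also leaves fewer observed events in a very small sample. Because SAP 5.1 calculates a median only when at least 50% of subjects reach the event, some sensitivity medians may not be estimable.
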